### **3.2.1 Study events description**

Dyads will be in the study for a total of nine weeks from enrollment to the follow-up visit. Screening occurs at least weekly and prior to enrollment. Enrollment and initial study measure completion, including first hair sample collection from both parent and adolescent, will occur at the beginning of Week 0. Parents will fill out the Medication Log during Week 0 in order to have a baseline of pain and anxiety medications before study intervention begins. The parent will receive Reiki training, a poster with suggested hand positions and a commercially-available book about Reiki in the home on the first day of Week 1. A visit window is defined as a week (7days) -1/+3 days from the initial Reiki training. During Week 2 the parent will receive a Reiki booster session with a repeat of the training and may ask questions. The parent will administer at least 5 times per week for at least 10 minutes each session. During weeks 1-4, the parent will collect saliva samples for themselves and their adolescent before and after any two Reiki sessions as long as they are collected on two separate days. At the end of Week 4, measures will be repeated either in person or by phone. During Week 8, measures will be repeated, the second hair sample obtained from both parent and adolescent, and the parent will participate in a qualitative interview. The qualitative interview will be administered in person by trained OSU College of Nursing

study staff as part of the interview session. Interviews will be audio recorded using a hand-held audio recording device. Audio recordings will be transcribed verbatim. Audio recording is voluntary and participants can choose to not have their interview recorded and still be a part of the study. See Appendix 2 for schema.

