salivary cortisol. A four-week follow-up period was chosen in order to obtain an accurate measure of HCC to determine any change in stress during the intervention period. Approximately 10-75 mg of hair is cut from the posterior vertex region of the scalp as close to the scalp as possible. The posterior vertex has the lowest variation in cortisol levels, and is the preferred area for sampling. Co-I ([name]) will train the PI and Co-I ([name]) on hair collection. We will take one cut at the first home visit (T0) and another at the four-week follow-up home visit (T2). Assay: Each 1 cm of hair approximates the mean cortisol level over the prior 1 month. Samples are assayed in duplicate and inter- and intra-assay coefficients of variation calculated. HCC levels are expressed in hair as pg/mg.

Saliva collection and assay: Salivary alpha amylase (sAA) is a non-invasive biomarker that detects immediate changes in autonomic nervous system response, signaling a change in level of stress. Interventional studies have shown a decrease in sAA levels as a response to an intervention meant to stimulate relaxation. Collection: The Salimetrics Drool Tube for adults will be used for saliva collection from the parents and cognitively aware adolescents. The SalivaBio Swab for infants will be used for the remaining adolescents to eliminate any choking hazards. Samples will be collected for both parent and adolescent pre and post two Reiki sessions per week for four weeks. Storage: The swab will be placed in a Swab Storage Tube. Tubes will be put into a sealable plastic bag marked as parent or adolescent, the date and time of collection, and put into the home freezer until the PI or other team member collects them at the follow up visit. Samples will be transported on dry ice to the lab, and frozen at -20C until processed. Assay: The saliva samples will be batch processed after thawing using the Salimetric Alpha Amylase assay following manufacturer's instructions. The amount of alpha-amylase activity present in the saliva sample is directly proportional to the increase in absorbance at 405 nm.

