The primary outcome for the proposed study is the feasibility and acceptability of teaching Reiki to parents of adolescents receiving palliative care. Secondary outcomes include: adolescent global health, pain interference, medication use, and stress measures of hair cortisol (chronic, long term) and alpha amylase (immediate, short term); and parent symptom profile (depression, anxiety, physical function, pain interference, fatigue, sleep disturbance and ability to participate in social roles and activities), and stress measures of hair cortisol (chronic, long term) and alpha amylase (immediate, short term).

Because Reiki has not been taught to parents of adolescents receiving palliative care at home, we will determine the feasibility and acceptability of this intervention through calculating the percentage of dyads approached to the total participants who consented to participate in the study as well as completed the study. We will also conduct qualitative interviews with parents to examine what they thought of the teaching protocol, the usefulness of Reiki for stress and other symptoms, as well as their thoughts on the study as a whole. Secondary outcomes will be collected in order to explore preliminary evidence on overall health and quality of life as well as medication use for the adolescents and overall quality of life and symptoms of the parent.

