### **3.2.2 Exposure/Outcome measures and instruments**

The main data collection will occur during enrollment (T0), end of the intervention period, Week 4 (T1), and the follow up visit in Week 8 (T2). Parents will be instructed on how to collect and store alpha amylase saliva samples for themselves and their adolescent. Collection: The Salimetrics Drool Tube for adults will be used for saliva collection from the parents and cognitively aware adolescents. The SalivaBio Swab for infants will be used for the remaining adolescents to eliminate any choking hazards. Samples will be collected for both parent and adolescent pre and post any two Reiki sessions on two separate days per week for four weeks. Storage: The swab will be placed in a Swab Storage Tube. Tubes will be put into a sealable plastic bag marked as parent or adolescent, the date and time of collection, and put into the home freezer until the PI or other team member collects them at the follow up visit. Samples will be transported on dry ice to the lab, and frozen at -20C until processed.

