## **3.3 Interventions**

This is a one-group feasibility study. There is only one intervention group. The Overall-Study PI and Local PI will recruit professional Reiki practitioners who are trained at Level 3 or Master Level and have prior experience working with families and children. A Reiki Master will perform the initial teaching and instruct the parent how to perform a simple 15-minute Reiki session. Parents will complete a return demonstration using light touch with their adolescent. The parent will receive an introductory book on Reiki, an informational article, and a poster showing hand positions for their reference as well as the intervention log to record sessions. The initial teaching session will take about 1.5 hours with breaks. The initial teaching session will be conducted by a Reiki Master and will mark the beginning of Week 1. A Reiki practitioner (Master or Level 3) will provide a shorter "booster" session the following week to review techniques with the parent and answer questions. This session will last 45 minutes with breaks. The "booster" session will count as one day for that week. Parents will be asked

to complete a minimum of 15 minutes of Reiki with their adolescent at least five days per week for the four-week intervention period. Parents will receive a phone call from the research coordinator once per week during weeks three and four to check in with them and ask if they have any questions or problems with the intervention and will refer to a Reiki practitioner if needed.

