#### 4.1.1 Sample size

We will enroll 12 adolescent-parent dyads in order to achieve study objectives. The emphasis is on Aims 1 and 3, the feasibility and acceptability of the study as well as the parents' feelings about learning Reiki and their ability to help their adolescents. These aims will inform future study protocols. Aim 2 is exploring both parent and adolescent stress, symptoms, and overall quality of life. We are also testing data collection of hair and saliva in this population of adolescents receiving palliative care in the home. The preliminary results from the primary and secondary outcomes will inform the sample size of the next planned study, a two-group randomized controlled trial.

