# 6 Safety Considerations

## 6.1 Risks

The risk of participating in this study are minimal. Reiki is non-invasive and can therefore be used with anyone. NCCIH considers Reiki to be safe although little scientific evidence exists about its effectiveness. There is the possibility that either the parent or adolescent may become uncomfortable during the Reiki session. If this happens, they should either take a break or change positions to be more comfortable. There is a risk for becoming tired or having pain due to the adolescent's illness during the Reiki session. If either of these happens, the dyad should take a break and/or change positions to one that is more comfortable. Some of the data collection may be uncomfortable or inconvenient for the parent and/or adolescent. The hair sample collection may cause a slight physical discomfort due to the gentle pull on the hair before cutting and may cause social discomfort if the parent or adolescent feels as though the small bare spot on the scalp where the hair was clipped may show. Any study personnel who will be collecting hair will be trained to perform the sample cut gently and in a spot not likely to show. Collecting the saliva samples may be inconvenient for the parent as two samples must be collected (pre and post) for both the parent and adolescent (four samples total each time) twice per week for four weeks and stored in the home freezer. We will provide pre-labeled sample tubes and baggies so that the parent only has to add the date to each baggie in order to decrease the inconvenience as much as possible.

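### Parents may pick which two Reiki sessions a week to sample for saliva; if the pick follows tension or calm, regression to the mean can create or hide an amylase change.

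*Combined protocol and SAP*

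**What the plan says.** Section 3.2.1 has the parent collect saliva from both members of the dyad "before and after any two Reiki sessions as long as they are collected on two separate days". Section 3.2.2 repeats the rule and adds the frequency: "pre and post any two Reiki sessions on two separate days per week for four weeks". Separate days is the only restriction.

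The pool to choose from is also set in section 3.2.1: "The parent will administer at least 5 times per week for at least 10 minutes each session". Section 3.3 gives a different minimum session length (15 minutes) but likewise asks for five days a week. The two lengths must be reconciled, since they affect the interval between the pre and post samples, but the count of about five sessions is not in dispute.

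Table 1, the saliva paragraph in section 3.2 and section 6.1 add only counts. No section assigns sessions beforehand, fixes a time of day or asks why a session was sampled. The Parent Intervention Log in Appendix 3 has columns for date, start time, minutes, interruptions, place and comments. It has no mark for sampled sessions and no rating of tension before the session.

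Section 3.2 lists "alpha amylase (immediate, short term") as a secondary outcome for adolescent and parent, and describes the marker as one that "detects immediate changes in autonomic nervous system response, signaling a change in level of stress". Section 3.3 states: "This is a one-group feasibility study. There is only one intervention group".

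**The concern.** The marker responds to the state of the moment, and the person choosing the moment can see that state. A parent who tends to sample when the adolescent or the parent is tense will collect pre-session values that are high by selection. The post-session values will then be lower on average even if Reiki does nothing. A parent who samples at calm moments, perhaps because collection is easier then, produces the opposite shift and could mask a real fall. In a one-group study neither can be told apart from the effect of a session.

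Amylase is the only quantitative measure of immediate response; the log's comments on each session are the only other immediate record. Section 3.2 cites studies in which amylase fell after relaxation interventions, so a fall here would invite that reading. Section 4.1.1 adds that primary and secondary results will inform the sample size of the planned randomized trial, so a distorted change could carry forward into that calculation.

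**Working it through.** The plan gives no expected amylase change, SD or correlation, so there is no figure of its own to reproduce.

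**Inputs from the documents**
- Dyads: 12 (section 4.1.1: "We will enroll 12 adolescent-parent dyads in order to achieve study objectives").
- Sampled sessions: 2 a week for 4 weeks, so 2 x 4 = 8 per dyad.
- Sessions to choose from: at least 5 a week, so at least 5 x 4 = 20. The sampled share is at most 8/20 = 40%.
- Tubes: section 6.1 gives "four samples total each time", so 4 x 8 = 32 per dyad.

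**Assumptions, not in the documents**
- No Reiki effect.
- r, the within-person correlation between the feature that drives the choice and the pre-session amylase level: 0.25 to 0.5.
- rho, the within-person correlation between pre and post values: 0.5.
- Between-person SD of the true change: 0.3 to 0.5 within-person SD.
- A two-sided t-test at 0.05 on each person's mean change. Section 4.1 does not contain this test. Its t-tests compare T0, T1 and T2, when no saliva is taken.

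**Expected change.** If the two highest of five sessions on the driving feature are sampled, their mean is 0.829 SD above the person's average (expected mean of the top two of five standard normal values). With regression to the mean,

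expected change (post minus pre) = -(1 - rho) x r x 0.829.

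- r = 0.25: -(0.5)(0.25)(0.829) = -0.10 within-person SD.
- r = 0.5: -(0.5)(0.5)(0.829) = -0.21 within-person SD.

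Choosing the two calmest sessions reverses the sign.

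**False-positive rate.** This was simulated with 12 people, 4 weeks and 2 of 5 sessions under the assumptions above. Ranges cover the two between-person SDs.

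| How parents choose | Mean spurious change, r = 0.25 / 0.5 | False-positive rate, r = 0.25 / 0.5 |
|---|---|---|
| Unrelated to state | 0 / 0 | about 5% / about 5% |
| All 12 in the same direction every week | -0.10 / -0.21 | about 9-11% / about 19-30% |
| One-third on distress, the rest unrelated | -0.03 / -0.07 | about 5-6% / about 6-7% |
| Each parent equally likely to favour tense or calm | about 0 / about 0 | about 5% / about 5% |

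The one-third row follows from the row above it: 0.10/3 = 0.03 and 0.21/3 = 0.07.

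**What naming sessions in advance achieves.** With the sampled sessions fixed without regard to state, the mean change is 0.00 and the rate is about 5%. This holds only if the Reiki sessions are not themselves timed to distress. As an illustration, suppose Reiki is given at the 5 most distressed of 14 possible moments a week and 2 of those 5 are sampled at random. With r from 0.2 to 0.6, rho from 0.3 to 0.7 and no between-person variation, the spurious change is still -0.06 to -0.41 SD (-0.20 at r = 0.4, rho = 0.5).

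**The case against.** The strongest reply is that nothing in the documents says parents choose saliva sessions by distress. The background sections report that parents in an earlier study wanted to be able to give Reiki when it was called for. That concerns the wish to learn Reiki, not which sessions are sampled. Convenience is at least as plausible a driver, given the burden that section 6.1 acknowledges. This stands: the bias is conditional and even its direction is unknown.

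It also stands that the larger error rates need every parent to lean the same way every week. When directions are mixed, or only some parents select, little inflation remains.

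A reader might push the other way and infer that false positives are the likely outcome. Setting r = 1.0 gives a drop of 0.5 x 1.0 x 0.829 = 0.41 SD and rates above one-half. The documents do not support that case. It requires the parent to rank sessions perfectly on an enzyme level that is assayed in batch later. One choice of session also serves both people, so it cannot track both pre-session levels perfectly unless those coincide.

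Two further points have partial force. Sections 3.2 and 3.2.2 label samples with date and time, and the log holds date and start time, so sampled sessions can usually be identified by matching. However, section 6.1 says only the date need be added, and identifying a session does not show why it was chosen. Finally, this is an openly uncontrolled feasibility study, and the primary outcome is untouched. That limits the importance of the point, but section 4.1.1 still gives the secondary results a use beyond this study.

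**Conclusion.** The free choice of sessions is real, and nothing elsewhere in the protocol restricts it beyond separate days. If choices lean towards tense or towards calm moments, the pre/post amylase change will be biased, and a one-group design cannot reveal it.

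The documents do not fix the size. Under the stated assumptions it runs from none (mixed directions, about 5% false positives), through slight (one-third selecting, about 5-7%), to a change of 0.10 to 0.21 within-person SD with about 9-30% false positives if all parents select alike. These rates describe an assumed test, not one in section 4.1.

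The documents do not support the inference that an amylase fall in this study would be a selection artefact. They support only that it could not be told apart from one. The affected outcome is an exploratory secondary one. The change is worth making because it is cheap and the results are meant to inform the next trial.

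**What to change.** In sections 3.2.1 and 3.2.2 and in the parent instructions, replace the free choice with sessions named in advance. An example is the first Reiki session on each of two weekdays set with the family at T0, or the next session held if there is none that day. Add a column to the Parent Intervention Log to mark sampled sessions and note any departure. Reconcile the date-and-time labelling in sections 3.2 and 3.2.2 with the date-only instruction in section 6.1, so that clock time is recorded.

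The cost is about one sentence in each place and slightly less flexibility for families. The number of tubes stays at 32 per dyad.

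State the limit openly. The parent still decides when the first session of the day takes place, and the fallback to the next session leaves some choice. The change therefore does not remove bias if Reiki is itself timed to distress. The report should say that an uncontrolled pre/post fall in amylase is not to be read as an effect of Reiki.

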### **3.2.2 Exposure/Outcome measures and instruments**

The main data collection will occur during enrollment (T0), end of the intervention period, Week 4 (T1), and the follow up visit in Week 8 (T2). Parents will be instructed on how to collect and store alpha amylase saliva samples for themselves and their adolescent. Collection: The Salimetrics Drool Tube for adults will be used for saliva collection from the parents and cognitively aware adolescents. The SalivaBio Swab for infants will be used for the remaining adolescents to eliminate any choking hazards. Samples will be collected for both parent and adolescent pre and post any two Reiki sessions on two separate days per week for four weeks. Storage: The swab will be placed in a Swab Storage Tube. Tubes will be put into a sealable plastic bag marked as parent or adolescent, the date and time of collection, and put into the home freezer until the PI or other team member collects them at the follow up visit. Samples will be transported on dry ice to the lab, and frozen at -20C until processed.

### **3.2.3 Data management**

Data will be collected using either paper measures or electronic measures via iPad per patient preference and/or internet availability. Data collected electronically will use Research Electronic Data Capture (REDCap) and entered by study staff into the study-specific electronic database for analysis. To minimize risks of disclosure of participants' personal information, the study site will ensure management and protection of materials and information in compliance with national, state and institutional guidelines for protection of confidentiality of health-related research information. Any paper measures will be checked for completeness during collection by the study team member collecting the data. The Medication Log and the Parent Intervention logs will be paper only. Study staff will collect a snapshot of the de-identified medication log and intervention log periodically in coordination with study visits. If the Medication Log is blank, parents will be asked if they have given any pain or anxiety medications during the previous period and have the parent fill out the log if needed. If the Intervention Log is blank or does not contain at least 5 entries for the previous week, parents will be asked about Reiki sessions and will fill out the log if needed. Data collected on paper will be scanned and emailed to the PI via secure email when each participating dyad has completed the follow-up visit. Data entered from paper measures will be entered into a database using double data entry and checking.

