### 3.2 Study measures and outcomes

Table 1: Measures and Timing

Variable (source) # = adolescent, * = parent	T0: Enrollment	T1: End of Intervention	T2: 4-week Follow up
Demographics##	X		
PROMIS Pediatric Global Health 7+2 or Parent Proxy Global Health 7+2#	X	X	X
PROMIS Pediatric Pain Interference or Parent Proxy Pain Interference#	X	X	X
Parent: (physical and emotional) PROMIS 29 Symptom Profile*	X	X	X
Hair Sample Collection##	X		X
Parent Experience of Providing Reiki*			X
Saliva collection##	Pre/post 2 Reiki sessions per week during weeks 1-4		
Medication Log#	Completed during weeks 0-4		
Parent intervention Log*	Completed during weeks 1-4		

Demographic form (T0) basic demographic information on both parent and adolescent.

Patient Reported Outcomes Measurement Information System (PROMIS), sponsored by the NIH. *PROMIS Pediatric Pain Interference* or *PROMIS Parent Proxy SF Pain Interference*, assesses how pain interferes with daily life for the adolescent. Well-validated measures show significant correlations between child and parent reports of pain. We will use the *PROMIS Pediatric Global Health 7+2* measure to obtain an overall evaluation score of the adolescents' physical and mental health. Both self-report and parent proxy versions are valid and reliable. Adult profile PROMIS 29 Symptom Profile (parent) assesses seven domains (depression, anxiety, physical function, pain interference, fatigue, sleep disturbance and ability to participate in social roles and activities).

Medication Log documenting all pain medications given one week prior to and during the intervention period.

Parent Intervention Log provided for parent record keeping. These logs will document Reiki session details, including the date, time, and length of session, interruptions to session, where the session took place, and parent comments and reactions (including adolescent reactions).

Hair collection and assay: Hair cortisol concentration (HCC) is a measure of chronic stress. A recent study found that the mean cortisol level assayed in 1 cm of hair was correlated ( $r=0.61$ ,  $p<0.01$ ) with the mean

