## 4 Statistics and Data Handling

### 4.1 Statistical considerations

Primary outcomes (Aims 1): Feasibility will be examined by computing the proportion of approached subjects enrolled in the study, the proportion of subjects who complete Reiki training, and the proportion of enrolled subjects' who completed data collection. Qualitative data will be analyzed using a basic qualitative descriptive approach. Qualitative data (audio recorded interviews and field notes) will be transcribed verbatim, checked for accuracy, imported into Atlas.TI for data management, and analyzed. Portions of text are labeled or coded with terms that are descriptive of the user opinions and observations. Codes will be identified and defined in an iterative process by investigators independently coding the data and arriving at agreement in discussion/review. Codes are sorted and categorized into themes, which will be discussed in research meetings. We will use mixed methods to triangulate the qualitative and quantitative data to produce a more accurate picture of parental beliefs and experiences. These results will be used to refine procedures for future, larger studies. Qualitative results will be triangulated with quantitative results to answer questions of feasibility. Qualitative results will also be examined to explore the parents' confidence in delivering Reiki and beliefs in their ability to help their adolescent (Aim 3).

Secondary outcomes (Aim 2): Descriptive statistics will be used to check data distribution, identify outliers, examine the balance in baseline measurements, and report outcome measures (e.g. pain) at each time point. Trend plot will be used to visualize the trend of change over time. Pair-wise comparisons will be conducted to test the difference in the change in outcome measures (T0 versus T1, T1 versus T2, T0 versus T2) using two sample t-tests. We will not adjust for multiple comparisons to avoid further reduction of power. Mixed effect modeling for repeated measures will be used to examine the trajectories of treatment effect over time, adjusting for within-patient clustering from repeated measures and possible confounders.

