## Pain and Anxiety Medication Log

**Subject ID** \_\_\_\_\_

Subject ID \_\_\_\_\_

Parent Intervention Log

Date	Start Time	Session Minutes	Any Session Interruptions?	Where did the session take place?	Comments/Reactions to Session

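### The Reiki log is queried only when a week shows fewer than five entries and additions are not marked, so the query can only leave the recorded count unchanged or raise it

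*Combined protocol and SAP*

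**What the plan says.** The Parent Intervention Log is a paper record kept by the parent. Section 3.2 says of it: "These logs will document Reiki session details, including the date, time, and length of session". In Appendix 3 its columns run from date, start time and minutes through interruptions and place to "Comments/Reactions to Session". No column shows when an entry was written.

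Section 3.2.3 has staff take snapshots of the log from time to time, tied to study visits. It then sets the query rule, which covers a log that is empty or that "does not contain at least 5 entries for the previous week, parents will be asked about Reiki sessions and will fill out the log". The sentence goes on to limit this last step to where it is needed.

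The number in the trigger matches the number requested of parents. Section 3.2.1: "The parent will administer at least 5 times per week for at least 10 minutes each session". Section 3.3 asks parents "to complete a minimum of 15 minutes of Reiki with their adolescent at least five days per week for the four-week intervention period".

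The same paragraph of section 3.2.3 treats the Medication Log differently. That log is queried only when it is blank, with no numerical threshold.

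Section 4.1 names three feasibility proportions: enrolment among those approached, completion of Reiki training, and completion of data collection. It names no analysis of sessions delivered.

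**The concern.** A data query should not depend on whether the recorded value meets the target. Here it does: a parent with four entries is asked about sessions, and a parent with five is not asked under this rule. An honest parent may recall a session she forgot to log. A parent who senses that five is expected may supply one that did not happen, or was shorter than entered. Both look the same on the form.

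The log is the only full session-by-session record of Reiki delivered. Aim 1 concerns teaching parents Reiki for use with their adolescent, and section 4.1 says the results will refine procedures for larger studies. How often parents managed the requested sessions is something a 12-dyad pilot is well placed to teach, and this rule acts on exactly the weeks where they may have fallen short.

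**Working it through.** The documents give no expected adherence, adherence threshold or back-fill rate, so there is no figure to reproduce. The check is textual, followed by illustrations under stated assumptions.

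**1. Direction of the rule.** For one parent-week let T be true sessions, L entries logged at the time, and A entries added after the query. The recorded count is

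- R = L if L ≥ 5 (no query);
- R = L + A, with A ≥ 0, if L < 5.

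Section 3.2.3 describes no step that removes an entry, so R ≥ L always, and R > L is possible only in short weeks.

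**2. R ≥ L does not mean R > T.** Suppose entries made at the time are genuine. Split A into real recovered sessions and false additions, and let U = T − L be the unlogged true sessions. In a queried week

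R − T = (false additions) − (U − real recovered sessions).

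The sign depends on two quantities that the plan does not collect.

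**3. Upper-bound illustration.** Assume complete logging and false filling to exactly five in each of four weeks, giving 5 × 4 = 20 recorded.

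- True 3 per week: 3 × 4 = 12; 20/12 = 1.67, overstated by 67%.
- True 4 per week: 4 × 4 = 16; 20/16 = 1.25, overstated by 25%.

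**4. Complete logging, partial false filling.** Assume 7 possible days a week, a session on each day with probability p, and each slot short of five falsely filled with probability f. Then

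P(R ≥ 5) = P(T ≥ 5) + Σ P(T = t) × f^(5−t), t = 0 to 4, with T binomial(7, p).

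For p = 0.6, P(T ≥ 5) = 0.261 + 0.131 + 0.028 = 0.420. With f = 0.25: 0.420 + 0.290 × 0.25 + 0.194 × 0.0625 + 0.077 × 0.0156 + a negligible remainder = 0.506. For f = 0.50 and 0.75 the results are 0.624 and 0.785. So 42.0% of weeks truly on target would read 50.6% to 78.5%.

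**5. Incomplete logging.** Now assume each true session is logged at the time with probability 0.8 and, if queried, each missed one is recovered with probability 0.8. Share of weeks recorded with at least five sessions:

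| p | True | Before query | After, f = 0 | After, f = 0.25 | After, f = 0.50 |
|---|---|---|---|---|---|
| 0.5 | 22.7% | 9.6% | 19.5% | 28.1% | 42.4% |
| 0.6 | 42.0% | 19.5% | 36.9% | 45.7% | 58.3% |
| 0.7 | 64.7% | 33.6% | 58.3% | 65.4% | 74.4% |

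At p = 0.6 the unqueried log is 42.0 − 19.5 = 22.5 points too low. After the query the error is 5.1 points low (f = 0), 3.7 high (f = 0.25) or 16.3 high (f = 0.50), so the query helps in all three cases. At p = 0.5 and f = 0.50 the error grows from 22.7 − 9.6 = 13.1 points low to 42.4 − 22.7 = 19.7 points high, so there it harms.

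**6. Other traces of use.** Saliva is collected around two sessions a week: 2 × 4 = 8 of 5 × 4 = 20 target sessions, or 40% at most. The practitioner's booster accounts for one day in Week 2. The Week 8 interview asks how often Reiki is used, which is again parent recall.

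**7. A related inconsistency.** Sections 3.2.1 and 3.3 differ on minutes per session (10 against 15) and on times against days per week. Over 20 sessions that is 20 × 10 = 200 against 20 × 15 = 300 minutes. The two must be reconciled before any summary of weeks on target can be read.

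**The case against.** The strongest reply is that this is ordinary recovery of missing data. The parent completes the log only where needed, and nothing tells her to reach five. Step 5 shows that the query can bring the count closer to the truth. That stands. A reader might infer that the rule turns true shortfalls into apparent compliance, or that it always biases delivered Reiki upwards. The documents support neither: both need false entries, or more false entries than unrecovered real ones, and nothing in the plan shows that.

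A second reply is that other checks exist. An early snapshot could be compared with the final log; saliva samples carry dates; paper measures are checked for completeness at collection whatever the count; and section 4.1 says: "Qualitative results will be triangulated with quantitative results to answer questions of feasibility". So it would be too strong to call the log the only evidence of use, or to say that fuller weeks are never looked at. But these checks are partial. The plan does not say whether a snapshot is taken before the query, nor that it is compared with the final log. Saliva dates cover at most 40% of target sessions, and the interview relies on recall.

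A third reply is that no named analysis changes. This also stands. The feasibility proportions in section 4.1 do not use session counts, nor do the Aim 2 comparisons and mixed models as described. A reader might infer that the primary outcome or the Aim 2 results are compromised; the text gives no basis for that.

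**Conclusion.** The point holds as a limited flaw in data collection. From the wording alone, the query is triggered by falling short of the requested weekly number, its additions are unmarked, and it can only hold or raise the count in short weeks. Its net effect relative to the truth is unknown in size and in direction. The 25% and 67% figures are upper-bound illustrations that assume complete logging and false filling to five. The milder scenarios run from a clear improvement to a clear overstatement, depending on a false-fill rate that the plan cannot reliably estimate.

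What is affected is the description of sessions and minutes delivered, and the use of that description in planning the next trial. The change is worth making because it costs little and cannot be made afterwards: once unmarked additions are in the log, they cannot be reliably separated.

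**What to change.** In section 3.2.3:

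- Replace the threshold trigger with one neutral question to every dyad at every log check, whatever the entry count and without citing five: *Is anything in the log missing or wrong?*
- Copy the log before asking.
- Add a column to the Parent Intervention Log: *added at check (date)*.
- In section 4.1, state that sessions and minutes will be reported with and without added entries, side by side, naming neither in advance as the true figure. Entries made at the time miss real sessions, and completed logs may include false ones.
- If reasons for missed sessions are wanted, ask about barriers in every week. Asking only in short weeks would bring back the one-sided trigger.

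The cost is one form column, a brief question at each check and one more line in the summary table. Recovery of forgotten sessions is kept, and it becomes visible.
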